# 1.0 Objectives\*

1.1 The purpose of this study is to study the effects of core activation on knee joint loading during ambulation in patients with knee osteoarthritis (OA). This study aims to investigate the effects of transversus abdominis (TA) activation during simultaneous kinetic analysis of time to initial peak ground reaction force (T1) at the heel in the sagittal plane.

The objective of this study is to determine whether patients with knee OA demonstrate changes in  $T_1$  during comfortable gait speeds when actively contracting the TA muscle. In addition, this study will serve as a pilot study in order to perform a post-hoc power analysis for future study on the effects of the independent variable (TA contraction/changes in core stability) on the dependent variable ( $T_1$ ).

1.2 Null hypothesis: There will be no change in  $T_1$  in patients with knee OA during gait while contracting their TA.

Alternate hypothesis: There will be a decrease in  $T_1$  in patients with knee OA during gait while contracting their TA.

# 2.0 Background\*

- 2.1 This will be the first study on this topic performed by the investigator. Regarding current knowledge gaps, evidence has shown an influence of core strength measures/stability on lower extremity function. This relationship has been examined very little in patients with knee OA; however, evidence does show a correlation exists. There have been no studies examining the effect of a core strengthening/stability intervention on lower extremity kinetics in patients with knee OA to the PIs knowledge.
- 2.2 This is the first study examining the effects of TA contraction knee loading during gait in this population.
- 2.3 Current evidence shows that core activation/stability may play a role in lower extremity kinetics and kinematics. Most research has focused on younger, more athletic individuals. Research on this population has in the past looked at patellofemoral disorders or ligamentous injury. For example, decreased core function has been shown to increase the risk of sustaining anterior cruciate ligament injury. In addition, increased core stability has resulted in decreased knee loading during athletic activities.

There continues to be an overall paucity of research on proper prescription

> and dosage of therapeutic exercise for patients with knee OA. Evidence has shown that quadriceps strengthening and aerobic conditioning do lead to decreased disability. Additionally, correlations have been shown between core stability and functional ability as measured via the Western Ontario and McMaster Universities Osteoarthritis Index. Patients with knee OA also exhibit decreased overall core stability as compared to healthy controls. This body of research however does not include any evidence on the effects of a core stability intervention on improving overall function.

> Knee OA leads to abnormalities in kinetic loading of the lower extremity during ambulation. An increase in  $T_1$  in this population has been observed when comparing to healthy controls. Separately, studies have shown that in patients with knee OA, knee joint loading can be influenced by intraarticular hyaluronic acid injections, resulting in decreased  $T_1$ . Therefore, this study will explore the idea of how activation of a muscle (TA), which plays a large role in core stability, influences kinetic loading ( $T_1$ ) during ambulation in patients with knee OA.

### 3.0 Inclusion and Exclusion Criteria\*

- 3.1 The PI will screen potential participants either in person, via medical record review (TherapySource in Rehabilitation Faculty Practice Clinic), or via phone conversation. The PI will also ask other clinicians if they are aware of anyone who may meet the inclusion criteria who may be willing to participate.
- 3.2 Inclusion criteria for the study will include those with medical diagnosis (providing written evidence from a physician, physician assistant, or nurse practitioner) of knee OA unilaterally or bilaterally. Exclusion criteria for the study will include: bilateral total knee arthroplasty, requirement of an assistive device or assistance with ambulation, spinal diagnoses which contraindicate participation in spinal stabilization activities, and those currently limited by another lower extremity pathology at the time of participation.
- 3.3 The following populations will be excluded from participation. Adults unable to consent may have difficulty following the cues to activate the TA while ambulating. Pregnancy women and younger individuals do not typically present with knee OA. Prisoners are admitted for treated in the School of Allied Health Professions (SAHP) as they are all served by University Health facilities.
  - Adults unable to consent
  - Individuals who are not yet adults (infants, children, teenagers)

- Pregnant women
- Prisoners
- 4.0 Study-Wide Number of Subjects\*: NA
- 5.0 Study-Wide Recruitment Methods\*: NA

#### 6.0 Multi-Site Research\*: NA

#### 7.0 Study Timelines\*

7.1 Each participant will only be required to participate for one session, lasting about 1 hour. This does not included the informed consent process requiring approximately 30 minutes of their time prior to participation. Approximately 5 months will be required to enroll all participants. It is the PI's goal to complete primary data analysis no more than 3 months after data collection is complete, so total estimated study time is 8 months.

#### 8.0 Study Endpoints\*

- 8.1 The primary study endpoint will be the cessation of data collection and the participants' active participation in the research program. The Secondary endpoint will be the completion of data analysis, which concludes the management of PHI.
- 8.2 Primary (exposure to any physical risk) and secondary (management of PHI) safety endpoints are synonymous with the study endpoints mentioned in 8.1.

#### 9.0 Procedures Involved\*

- 9.1 This project serves as pilot study for future investigation on the role of core stabilization on gait kinetics in patients with knee OA. Therefore the sample size will be small. Post-hoc power analysis will inform the PI about requirements for participant recruitment needs for future investigations.
- 9.2 After informed consent is completed, participants will be scheduled for a session in the Motion Analysis Laboratory in the SAHP. Patients will have already been asked to wear close fitting, exercise appropriate clothing to allow marker placement, and prevent marker blocking during motion analysis. Data collection will begin by collecting the following anthropometric data: body weight (pounds, converted to kilograms) via a scale, height (inches, converted to mm) via a tape measure, leg length from ipsilateral anterior superior iliac

spine to ipsilateral medial malleolus bilaterally (cm) via tape measure, and knee and ankle joint widths (cm) via a caliper. After collection of this data is completed and recorded, the PI will place reflective markers on the patient's skin via adhesive tape made for this purpose at the following landmarks bilaterally: ASIS, posterior superior iliac spine, lateral thigh, knee center of rotation, lateral leg, heel, lateral malleolus, and base of the second metatarsal. When this set-up is complete, static calibration of the motion analysis system will take place with the participant standing still in the capture area. When this is complete, the participant will be allowed a 2-minute warm-up by walking back and forth in the capture area. When this is completed the participant will be asked to walk at a comfortable pace across the capture area. Three trials with good force plate contact will be collected. After these three trials are obtained, the patient will lie supine on the mat in the lab, and will be taught how to perform a TA contraction. A Pathway MR-20 biofeedback device (The Prometheus Group, Dover, NH, USA) with two electrodes will be placed just medial to the ASISs on the participant's abdomen. A baseline maximal contraction will be performed supine, and the amplitude of contraction will be considered maximal voluntary isometric contraction (MVIC). The device will be set to provide audible feedback at 50% MVIC. The task will be repeated seated, standing, then ambulating three practice trials on the capture area. The participant will then be instructed to perform an additional three comfortable paced ambulation trials with good force plate contact while contracting the TA enough to cause audible feedback via the biofeedback device. After completing these three trials, the biofeedback device and reflective markers will be removed, and the participant will have completed their active participation in the study.

Procedure/Test	Rate of Occurrence
Anthropometric Data Collection	1
Reflective Marker Placement	1
Biofeedback Placement	1
TA Contraction Trials with	At least once per body
Biofeedback	position
Walking Trials without TA	2
Contraction	3
Walking Trials with TA Contraction	3

Q	3	
/		

- Exclusion criteria prevent participation of those who require assistance or assistive devices for ambulation, so safety during ambulation is thus minimized. The adhesive tape used in placement of the reflective markers is intended for placement on skin. In regards to PHI, the PI will be the only investigator involved in recruitment, informed consent, and collection of anthropometric data. All documentation of these aspects of the study will be kept in the PI's office in a drawer, with both the office and drawer able to be locked. The motion analysis data will be stored and analyzed on the computer in the Motion Analysis Laboratory under password protection, with the lab able to be locked.
- A tape measure, body weight scale, Pathway MR-20 biofeedback device (The Prometheus Group, Dover, NH, USA) with two electrodes, and Vicon Vero 2.2 Motion Analysis System will be used.
- Please see that attached Excel worksheet that will be used on data collection.
- 9.4 There is no long-term follow up for this study.
- 9.5 NA

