# **10.0 Data and Specimen Banking\***

- 10.1 Data banking will be performed at the conclusion of this study in order to use for research or post-hoc power analysis. The repository will consist of the digital data collected during the study. Data will be stored for a period of three years, and may only be accessed via password through the computer in the Motion Analysis Laboratory. Only the PI will have access to this data, and will only use the data with additional IRB approval of a new protocol. Anyone else wishing to use the data must first ask the PI permission before initiating a new protocol.
- 10.2 Data to be stored is the raw digital data (kinetic and kinematic) and analyzed (T1) collected during motion analysis.
- 10.3 The PI, or another researcher after first asking permission of the PI, will have to submit an application to the IRB before using the stored data for any research purposes. After IRB approval of a new protocol, the password for the computer will be provided, and the researcher will have access to the raw data only. They will be responsible for any analysis that may be required for new variables.

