# **11.0** Data Management\* and Confidentiality

- 11.1 The three trials without and with TA contraction during ambulation will be analyzed to determine  $T_1$  for each trial. The average of the three trials under each condition will be calculated. Statistical analysis will include a repeated measures, two mean comparison (a paired-samples t-test or Wilcoxon signed rank depending on results of assumption analysis). Statistical analysis will be performed using the most up to date version of SPSS available to the PI.
- 11.2 The study is serving as a pilot study for post-hoc power analyses of the variables under consideration for future study.
- 11.3 The computer, which stores and analyses the raw kinetic data, is password protected. Only the PI and the faculty member in charge of the lab have the password. In addition, only the faculty of the SAHP has access to the lab via key entry. All participants will be given a code-identifier, with a key kept in the compliance binder for the study (also containing informed consent documentation). This compliance binder will stay in the PI's office in a locked drawer.
- 11.4 Once the raw data is saved on the computer, the files will be backed up on a flash drive which will also be kept in a locked drawer in the PI's office.
- 11.5
- Data will be stored on the computer in the motion lab, and analyzed data will be backed up on a flash drive locked and stored in the PI's office drawer.
- Data will be stored for three years per the data banking procedure noted in section 10.1-10.3.
  - See 10.1-10.3 for persons having access to the data.

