### 23.0 Local Number of Subjects

23.1 Three to five participants will be recruited for the purposes of this pilot study.

23.2 NA

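### The pilot's second aim relies on an undefined post-hoc power analysis of 3 to 5 paired T1 differences, which gives either no planning information or a planned N that is unreliable unless the true effect is large

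*Protocol*

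**What the plan says.** Protocol section 1.1 gives two aims. The first is to see whether T1 changes during gait with TA contraction. The second is that "this study will serve as a pilot study in order to perform a post-hoc power analysis for future study". Section 9.1 explains that the sample is small because this is a pilot, and gives the use of the result: "Post-hoc power analysis will inform the PI about requirements for participant recruitment needs for future investigations". Section 11.2 repeats the purpose ("The study is serving as a pilot study for post-hoc power analyses of the variables under consideration for future study"), and section 10.1 lists it as a reason for keeping the data ("Data banking will be performed at the conclusion of this study in order to use for research or post-hoc power analysis").

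The amount of data is also fixed. Section 23.1: "Three to five participants will be recruited for the purposes of this pilot study". Section 11.1 compares two paired means, with three walking trials per condition, and adds: "The average of the three trials under each condition will be calculated". Each participant therefore contributes one T1 difference.

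The protocol gives no alpha, target power, target T1 difference or SD for the future study, and does not say how the power analysis would be done.

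**The concern.** The protocol itself pairs a named tool with a sample size, and the two do not fit. Post-hoc power analysis usually means one of two things.

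- **Observed power of the pilot's own test.** This repackages the p-value and says nothing new about how many participants a later study needs.
- **The pilot's observed mean difference and SD entered into a sample-size formula.** With 2 to 4 degrees of freedom both inputs are very imprecise, and the planned N depends on the square of their ratio.

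At stake is the size of the follow-on study. A lucky pilot would suggest a handful of participants, and an unlucky one several hundred. A later analysis plan could add a rule for handling the imprecision, but it could not add information to 3 to 5 differences.

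**Working it through.** There is no derived figure in the protocol to reproduce: the 3 to 5 participants are not based on a calculation. The check is therefore how much 3 to 5 differences can tell a planner.

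**Inputs from the protocol.** n = 3 to 5 (section 23.1); one difference per participant (section 11.1); so df = n − 1 = 2 to 4.

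**Assumptions not in the protocol.** Normal differences; future study with two-sided 0.05 and 80% power; true standardized difference d (mean/SD of the paired differences) from 0.3 to 1.5.

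**1. Observed power.** If the pilot gives exactly p = 0.05, its t statistic equals the critical value c. Observed power is then P(|T| > c), with T noncentral t on n − 1 df and noncentrality c. The result is 0.557 at n=5, 0.577 at n=4 and 0.615 at n=3, whatever T1 did.

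**2. Observed mean and SD as inputs.** The estimate d̂ times √n follows a noncentral t with n − 1 df and noncentrality d√n. Planned N = ceil((1.96 + 0.84)²/d̂² + 1.92). Needed N is the smallest number of pairs giving 80% power by the exact noncentral t. Share of pilots whose planned N is within a factor of two of the needed N:

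| True d | Needed pairs | n=5 | n=3 |
|---|---|---|---|
| 0.3 | 90 | 25% | 20% |
| 0.5 | 34 | 33% | 27% |
| 0.8 | 15 | 46% | 35% |
| 1.2 | 8 | 74% | 59% |
| 1.5 | 6 | 89% | 82% |

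The last two rows look good partly because of a floor: when 6 or 8 pairs are needed, there is little room to plan less than half of that. At d = 0.5 the share would be 47% with 12 pilot participants and 68% with 30.

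Spread of planned N at d = 0.5, 10th to 90th percentile:

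- All pilots: 6 to about 640 (n=5) and 4 to 556 (n=3).
- Only pilots showing a decrease, the direction of the alternate hypothesis in section 1.2: 6 to about 310 (n=5) and 4 to about 275 (n=3). Pilots in the wrong direction make up 13% and 19%.

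**3. What the pilot says about the SD.** The 95% limits are SD × √(df/χ²), using the 97.5% and 2.5% chi-square quantiles. At n=5, √(4/11.14) = 0.60 and √(4/0.484) = 2.87. At n=4 they are 0.57 and 3.73, and at n=3, 0.52 and 6.28. Under normality these depend on n alone, not on effect size, alpha or power.

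**4. Target fixed independently, point SD from the pilot.** At d = 0.5 the share within a factor of two rises to 70% (n=5), 62% (n=4) and 52% (n=3). At d = 0.3 it is 66% (n=5) and 49% (n=3); at d = 0.8, 74% and 56%. This is clearly better, yet at d = 0.5 it still misses by more than twofold in 30% to 48% of pilots.

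**5. Target fixed, whole SD interval shown.** If the pilot SD happened to equal the true SD, the 95% limits translate into 14 to 262 pairs at n=5, 13 to 439 at n=4 and 11 to 1242 at n=3, around a needed 34.

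**The case against.** The strongest reply is that the method in step 2 is inferred. The protocol states no inputs, and the details of a power calculation for a later study can properly wait for an analysis plan or for that study's own protocol. This stands as far as it goes: missing detail is not the fault. What remains is that the protocol itself names post-hoc power analysis, on 3 to 5 differences, as the tool for one of its two aims, and neither usual meaning of the term serves that aim well.

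Three further limits are accepted.

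- A reader might infer that the planned N is useless in every case. The documents do not support that. They give no effect size, the comparison is within person on averaged trials, and a large standardized difference cannot be excluded. At 1.2 or more, most pilots would land within a factor of two.
- A reader might infer that the pilot alone will set the future N. Section 9.1 says only that the analysis will inform recruitment. Section 2.3 already mentions outside T1 evidence, and nothing rules out using it.
- The upper percentiles near 556 to 640 include pilots that went in the wrong direction. Without them the upper end is roughly halved. The share within a factor of two at d = 0.5 hardly moves (34% at n=5 and 27% at n=3).

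It is also fair to say that a small pilot is legitimate and that the alternative extracts little from it. The point is not a request for more participants. It concerns one use of the data.

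**Conclusion.** The point holds in a limited form. Observed power carries no planning information at any n. Using the observed mean and SD gives a planned N that is unreliable unless the true standardized difference is large: about a quarter to a third of pilots fall within a factor of two at 0.5, and about a third to under a half at 0.8, assuming normal differences, two-sided 0.05 and 80% power. The imprecision of the SD does not depend on the effect size: the upper 95% limit is 2.87 times the estimate at best (n=5) and 6.28 times at worst (n=3).

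It would go too far to conclude that the pilot is invalid or that its own test is compromised. Neither the participants nor the T1 comparison is affected, and any harm falls on a study not yet written. This is a low-priority improvement to the second aim.

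**What to change.** In Protocol sections 1.1, 9.1 and 11.2, and to match in 10.1, replace the reference to post-hoc power analysis with wording such as:

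> The pilot will estimate the SD of the participant-level T1 differences with its 95% confidence interval. The future sample size will use a smallest worthwhile T1 change fixed independently of the pilot's observed effect, and will be shown over a range of SDs within that interval, together with any outside SD information, not from the pilot point estimate alone.

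**Cost.** Wording in four places and one short calculation on data already being collected; no extra participants or visits. The investigator must name and justify a smallest worthwhile T1 change. Section 2.3 points to two places to look, without figures: an increase in T1 that "in this population has been observed when comparing to healthy controls", and evidence that "knee joint loading can be influenced by intraarticular hyaluronic acid injections, resulting in decreased" T1. The investigator must also accept that the pilot alone supports only a wide range for N (step 5), so outside SD information will probably be needed.

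Planning on a one-sided 80% upper limit for the SD (1.56, 1.73 or 2.12 times the estimate at n=5, 4 or 3) is best left out or shown as one scenario only. At d = 0.5 it lowers the chance of planning too few from 59–63% to about 20%, but it plans more than twice the needed N in 48%, 55% and 63% of pilots at n=5, 4 and 3, against 8%, 10% and 12% with the point SD.

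### As section 11.1 is written, a T1 difference read as knee loading is not distinguished from a difference in walking speed

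*Protocol*

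**What the plan says.** Section 1.1 opens with loading: "The purpose of this study is to study the effects of core activation on knee joint loading during ambulation". The variable that stands for it is a time, obtained by "simultaneous kinetic analysis of time to initial peak ground reaction force" at the heel, with no scaling to stance time or speed. Section 2.3 makes the same link, setting out to explore how a muscle "which plays a large role in core stability, influences kinetic loading", with T1 given in brackets as the measure. Section 1.2 hypothesises a decrease in T1. The objective in section 1.1 asks about T1 "during comfortable gait speeds when actively contracting the TA muscle".

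Section 9.2 fixes the sequence for everyone. After a 2-minute walking warm-up, "the participant will be asked to walk at a comfortable pace across the capture area", and "Three trials with good force plate contact will be collected". The contraction is then taught lying down with biofeedback, and "The task will be repeated seated, standing, then ambulating three practice trials on the capture area". Last come "an additional three comfortable paced ambulation trials with good force plate contact while contracting the TA enough to cause audible feedback".

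Section 11.1 derives T1 for each trial, averages three trials per condition and compares the two averages by a paired t-test or Wilcoxon signed rank test. It names no other variable for comparison. Section 10.2 stores raw kinetic and kinematic data but lists only T1 as analysed.

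**The concern.** If the time to a force peak depends on how fast a person walks, a faster second condition would shorten T1 and look like the hypothesised effect, and a slower one could hide a real decrease. Nothing in the protocol fixes, matches or reports speed, so a reader of the result could not tell whether participants loaded the knee differently or walked at a different pace.

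Two sources of a speed change need to be kept apart:

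- **Contracting with biofeedback.** A speed change caused by this belongs to the effect named in the objective (T1 at comfortable speed while contracting). It does not bias that effect, but it changes what the effect means for knee loading.
- **Order or practice.** A speed change from this source is bias, because the contraction walks always come second.

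What is at stake is the interpretation of a pilot whose purpose is to inform a later study. No consequence for the size of that study is claimed.

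**Working it through.** The protocol gives no T1, speed, SD, effect size, alpha or power, so there is no stated figure to reproduce. Steps 1 and 2 rest on the text. Steps 3 to 5 are illustrations on assumed inputs.

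**1. The two conditions side by side (section 9.2)**

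| | Without contraction | With contraction |
|---|---|---|
| Pace | comfortable, self-selected | comfortable, self-selected again |
| Trial accepted on | good plate contact | good plate contact, with the feedback sounding |
| Speed criterion | none | none |
| Walking in the capture area beforehand | 2-minute warm-up | warm-up, 3 recorded trials, 3 practice trials |
| Passes counted after the warm-up | 1 to 3 | 7 to 9 at the earliest |

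**2. What pairing and averaging remove**

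For participant i, write the paired difference in mean T1 as D_i = δ + g(Δv_i) + e_i. Here δ is the change at unchanged speed, g(Δv_i) is the part due to that person's change in speed between conditions, and e_i is noise. Pairing cancels stable differences between people, and averaging three trials shrinks e_i. Neither touches g(Δv_i) when the speed change is consistent within a condition. Section 11.1 analyses only D_i, so δ and g are reported as one quantity.

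**3. Possible size of g (assumed)**

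Assume T1 is proportional to speed^-b, with b = 0.5 to 1. The documents state no such relation; at b = 0 the concern would vanish.

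| Speed change | b = 0.5 | b = 1 |
|---|---|---|
| +5% | 1.05^-0.5 - 1 = -2.4% | 1.05^-1 - 1 = -4.8% |
| -5% | 0.95^-0.5 - 1 = +2.6% | 0.95^-1 - 1 = +5.3% |
| +10% | 1.10^-0.5 - 1 = -4.7% | 1.10^-1 - 1 = -9.1% |
| -10% | 0.90^-0.5 - 1 = +5.4% | 0.90^-1 - 1 = +11.1% |

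**4. Against the pilot's own noise (assumed SD)**

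Section 23.1 gives n = 3 to 5. If the SD of paired T1 differences is 10% of baseline, the standard error is 10/√3 = 5.77% to 10/√5 = 4.47%.

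- 5% speed change: 2.41/5.77 = 0.4 to 5.26/4.47 = 1.2 standard errors.
- 10% speed change: 4.65/5.77 = 0.8 to 11.11/4.47 = 2.5 standard errors.

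The answer turns on the SD. With two components of 3% each, the SD is √(3² + 3²) = 4.2%. A 5% shift in T1 is then 5/(4.24/√3) = 2.0 to 5/(4.24/√5) = 2.6 standard errors. The documents do not allow a choice between these cases.

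**5. What the added variables would show (assumed SDs)**

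The 95% CI half-width for a paired difference is t(0.975, n-1)/√n times the SD: 2.48 SD at n = 3, 1.59 SD at n = 4 and 1.24 SD at n = 5. If the SD of speed differences is 3% to 8%, the half-width is 7.5% to 19.9% at n = 3 and 3.7% to 9.9% at n = 5.

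If stance time is proportional to speed^-c, T1 as a percentage of stance varies as speed^-(b-c). The speed effect disappears when b = c. If b and c differ by 0.5 in either direction, a 5% speed change still leaves about 2.4% to 2.6%, and a 10% change 4.7% to 5.4%.

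**The case against.** The strongest reply is that T1 at comfortable speed is the stated target and that both hypotheses concern T1, not load at matched speed. That stands, and it is why comfortable pace and T1 in ms should remain primary. It does not cover the step from T1 to knee loading in sections 1.1 and 2.3.

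The fixed order also has a plausible reason: with the untaught condition first, the taught contraction cannot carry over into it. The warm-up is itself walking in the capture area. On a platform 24 ft (7.3 m) long (section 20.2), at an assumed 0.8 to 1.2 m/s, two minutes covers 96 to 144 m, or about 13 to 20 lengths, fewer with turns. So an order or practice effect is reduced. It is not excluded.

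A separate SAP and the data-collection worksheet mentioned in section 9.0 are not shown, and either might name speed. Section 11.1 says that the analysis will include the paired comparison, which leaves room for more. This lowers the weight of the point; the pace, the order and the loading interpretation are still fixed in the protocol.

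Three stronger readings might be inferred, and the documents do not support them:

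- **That speed and T1 cannot be separated at all.** Markers and force plates are recorded and the raw data are stored, so speed can be derived. The gap lies in the analysis as written.
- **That the audible cue biases the comparison.** The cue is how the contraction is delivered and verified, so it is part of the condition studied.
- **That the IRB rules in sections 10.1 and 10.3 would block a later speed analysis.** They govern banked data after the study ends. The primary analysis, planned within 3 months of data collection (section 7.1), is not restricted by them.

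**Conclusion.** The point holds and is minor. T1 is an unscaled time, measured at a pace chosen separately in two fixed-order conditions, and it is the only variable section 11.1 names for comparison. As written, the analysis does not distinguish a change in loading from a change in speed, although the recorded data would allow speed to be examined.

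No magnitude is established. The T1 shifts of 2.4% to 5.3% (5% speed change) and 4.7% to 11.1% (10%) rest on an assumed power relation. Their ratio to the pilot's noise rests on an assumed SD: with an SD of 10%, a 5% speed change lies within that noise. A reader might go on to infer that the pilot is likely to give a false positive or a false negative. The documents do not support that, because they give neither the size nor the direction of any speed change.

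**What to change.** Keep comfortable pace, the order of conditions, T1 in ms and the paired comparison as primary. Add to section 11.1:

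> Walking speed (from the pelvic markers) and stance time (from the same force-plate contact as T1) will be derived for each of the six trials and averaged by condition, as for T1. Each participant's speed, T1 in ms and T1 as a percentage of stance time will be listed by condition. Paired differences in speed and in T1 as a percentage of stance time will be reported with 95% confidence intervals as supportive, descriptive results. The T1 result will be interpreted as the effect at self-selected pace, not as a speed-independent change in knee loading. A non-significant speed difference will not be taken as equal speed.

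The cost is a little more processing of data already recorded, with no extra walks, equipment or participants; less is needed if the worksheet already captures speed. The limits should be accepted openly: intervals will be wide with 3 to 5 participants, an order effect is shown and not removed, and percentage of stance removes only proportional time scaling.
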